### **2.1.3 Recruitment Strategies**

It is estimated that new patient accrual will take approximately 2 years. Recruitment strategies may include IRB-approved advertising and direct contact with healthcare providers. Interested individuals may contact the NIH *Office of Patient Recruitment Clinical Research Center* via a toll-free [contact]) or email ([contact]) to be prescreened for the protocol using questions provided by the research team. Individuals who are deemed eligible by the patient recruitment staff will have their contact information forwarded to the study staff. Because of the frequency of visits to the NIH, subjects will be limited to the individuals living within North America.

## **2.2 SCREENING EVALUATION**

### **2.2.1 Pre-Screening**

Potential subjects will be asked to arrange for a referral letter from their local physician and a copy of their medical records to be sent to the clinical site. Based on a review of their medical records, further qualified subjects will be enrolled and evaluated on the Evaluation of Bone and Mineral Disorders protocol (01-D-0184), to exclude genetic causes of FGF23-mediated hypophosphatemia and confirm the diagnosis of TIO, and ensure that the tumor cannot be localized and/or easily resected.

### **2.2.2 Screening Visit**

Patients with a confirmed diagnosis of inoperable, metastatic, or non-localized TIO will be enrolled into this protocol by agreeing to and signing the informed consent and will undergo further eligibility screening (thoroughly evaluated based on the inclusion and exclusion criteria) at the NIH Clinical Center. This may be done as an inpatient or outpatient visit, at the discretion of the investigator and the subject. If eligible and the patient would like to begin drug immediately, the testing for the screening and baseline visits will be combined into a single inpatient visit. If not, the baseline visit and initiation of drug should occur within 6 weeks of the screening visit. Patients who have been previously treated with BGJ398 must be off BGJ398 for at least 2 weeks prior to the screening/baseline visit.

Procedures and tests during screening (if not combined with baseline visit) will include:

1. History
  - a. Detailed history of disease
  - b. Current medications including assessment of exclusionary medications/foods
2. Physical Exam
  - a. Height and weight measurement
  - b. Vital signs (pulse, blood pressure, temperature, and respiratory rate)
  - c. Physical examination
3. Blood tests
  - a. Blood chemistries: sodium, potassium, chloride, bicarbonate, creatinine, glucose, urea nitrogen, albumin, calcium, magnesium, phosphorous, alkaline phosphatase,

*Abbreviated Title: BGJ398 in TIO*

*Version Date: 21MAY2019*

- alanine aminotransferase (ALT), aspartate aminotransferase (AST), total bilirubin, direct bilirubin, LD, total protein, total CK, and uric acid
- b. Thyroid Stimulating Hormone (TSH) and Free Thyroxine (fT4)
- c. 25-OH vitamin D, 1,25 (OH)2-Vitamin D, intact PTH and FGF23 levels.
- d. Complete blood count (CBC): white blood cells (WBC), red blood cells (RBC), hemoglobin, hematocrit, mean corpuscular volume (MCV), red cell distribution width (RDW), and platelets.
- 4. Urine testing
  - a. Urine pregnancy test in females with childbearing potential.
  - b. Urinalysis: glucose, protein, urobilinogen, pH, hemoglobin, ketones, nitrite, leukocyte esterase, appearance, specific gravity, color, RBC, WBC, and squamous cells.
  - c. 24-hour urine for calcium, phosphorus, creatinine.
- 5. Imaging
  - a. FDG or Ga-DOTATATE PET/CT or Octreotide SPECT/CT if adequate study not done within the preceding 6 months.
- 6. Electrocardiogram to rule out exclusionary rhythm abnormalities.

## **2.3 REGISTRATION PROCEDURES**

### **2.3.1 For Participating Site Registration: NOT APPLICABLE.**

## **2.4 RANDOMIZATION (OR STRATIFICATION) PROCEDURES: NOT APPLICABLE.**

## **2.5 BASELINE EVALUATION (MAY BE COMBINED WITH SCREENING VISIT):**

Subjects who elected not to initiate BGJ398 at the screening visit will return to the NIH for an inpatient admission within 6 weeks of the screening visit to begin BGJ398 treatment. At that time, the following procedures and tests will be performed prior to the first dose:

1. History
  - a. Interim history
  - b. Current medications
2. Physical Exam
  - a. Weight and height measurement
  - b. Arm span and sitting height will be measured at baseline and 24-week visits
  - c. Vital signs (pulse, blood pressure, temperature, and respiratory rate)
  - d. Physical examination
3. Blood tests
  - a. Blood chemistries: sodium, potassium, chloride, bicarbonate, creatinine, glucose, urea nitrogen, albumin, calcium, magnesium, phosphorous, alkaline phosphatase, alanine aminotransferase (ALT), aspartate aminotransferase (AST), total bilirubin, direct bilirubin, LD, total protein, total CK, 25 OH vitamin D and uric acid

*Abbreviated Title: BGJ398 in TIO*

*Version Date: 21MAY2019*

- b. Complete blood count (CBC): white blood cells (WBC), red blood cells (RBC), hemoglobin, hematocrit, mean corpuscular volume (MCV), red cell distribution width (RDW), and platelets.
  - c. Bone turnover markers - collagen type I C-telopeptide (CTX) and Procollagen I Intact N-Terminal (P1NP) (baseline, 12-week, 24-week, 36-week visits)
  - d. 25-OH-Vitamin D (baseline, 24-week, and 36-week visits)
  - e. 1,25-OH2-Vitamin D, intact PTH, FGF23
  - f. Two-hour oral glucose tolerance test (baseline and 8-week visit)
4. Urine testing
    - a. Urine pregnancy test in females with childbearing potential.
    - b. Urinalysis: glucose, protein, urobilinogen, pH, hemoglobin, ketones, nitrite, leukocyte esterase, appearance, specific gravity, color, RBC, WBC, and squamous cells.
    - c. 24-hour urine for calcium, phosphorus, creatinine (at monthly NIH visits)
    - d. Spot urine for calcium, phosphorus, creatinine (local laboratory visits only)
  5. Imaging
    - a. Renal ultrasound (baseline and 24-week visit)
    - b. Echocardiogram (baseline, 8-week, and 24-week visit) Patients with a decline in ejection fraction will be monitored monthly with serial echocardiograms for resolution.
  6. Electrocardiogram (EKG) (screening and every 4-12 weeks depending on risk factors for long QTc)
  7. Questionnaires (described in section 3.5)
    - a. RAND SF36
    - b. PROMIS
  8. Rehabilitation Medicine Consultation
    - a. The Five Times Sit to Stand Test (lower extremity strength)
    - b. The grip strength test (hand dynamometer; upper extremity strength)
    - c. The Disabilities of Arm Shoulder and Hand Outcome Measurement (DASH).
    - d. Clinical rehabilitation evaluation (baseline, 24-week, and 36-week visits)
    - e. Six-minute walk test (baseline, 24-week, and 36-week visits)
  9. Placement of an indwelling catheter for frequent blood draws (baseline visit only)
  10. Ophthalmology Evaluation (baseline, monthly NIH visits while on BGJ398, 36-week, and as clinically indicated)
  11. With the first dose (time 0), the following tests are performed within the first 24 hours (baseline visit only):
    - a. Blood draw at time 0 and every 2 hours ( $\pm$  20 minutes) for phosphorous and creatinine
    - b. Spot urine at time 0 and every 2 hours ( $\pm$  20 minutes) for phosphorus and creatinine
    - c. Blood draw at time 0 and every 4 hours ( $\pm$  20 minutes) for FGF23, 1, 25 (OH)2-vitamin D, ionized calcium, iPTH.

*Abbreviated Title: BGJ398 in TIO*

*Version Date: 21MAY2019*

- d. Blood draw for pharmacokinetics at time 0 and 2, 4, 6, 8, 10 and 24 hours ( $\pm$  20 minutes) after the first dose.

All tests and procedures performed at the baseline visit will be repeated at the interval visits unless noted above. Pharmacokinetic samples will be repeated with fasting labs at the 4-week and 8-week visit. In patients with identifiable tumors and/or metastatic disease, the imaging study that best characterized their tumor(s) prior to BGJ398 will be repeated at the 24-week visit, if clinically indicated. See schedule of events in section 3.6.1 for more details.

### **3 STUDY IMPLEMENTATION**

#### **3.1 STUDY DESIGN**

Calcitriol (half-life is 5-8 hour) and phosphorous will be withheld for 3 days prior to the initiation of BGJ398 to allow for washout.

After initiation of study drug, subject will complete 24 weeks of BGJ398 with escalation/de-escalation of drug as described in Sections 3.1.2 and 3.3. Patients will return to the NIH every 4 weeks while on BGJ398 for an outpatient visit and labs per the schedule of events. Between monthly NIH visits, labs will be obtained per the schedule of events at the patients' local laboratories and results will be forwarded to the study team for review. In addition, any patient taking a concomitant medication associated with prolonged QT will obtain an EKG as an outpatient within 7-10 days after an increase in BGJ398 or the relevant concomitant medication. At the end of 24th week of BGJ398 treatment, subjects will be admitted as inpatients at the NIH for detailed laboratory and imaging evaluation as described in schedule of events. At the completion of the 24 weeks of treatment, patients who appear to have had a complete metabolic response will be evaluated at the NIH every 4 weeks for 3 additional visits. Complete metabolic response will be defined as normalization of blood phosphate and FGF23 levels after withdrawal of study drug. Local labs will be obtained in between NIH visits as clinically indicated on an as-needed basis. Subjects who have normal phosphate levels while on BGJ398 but have not had a complete metabolic response at the end of the 24 weeks of study drug may be considered for drug continuation in the extension phase, described in 3.1.3. Those who have not responded, have experienced significant side effects, or do not want to continue in the extension phase, will be terminated from the study and referred for other treatment.

During the active drug study period, subjects will not receive calcitriol and phosphorous supplements. However, subjects may be placed on calcitriol and phosphorous while in the post-BGJ398 drug monitoring phase or during dose interruptions, as clinically indicated. During the post-drug monitoring period calcitriol and phosphorous will be re-started on individual basis as clinically indicated (muscle weakness, bone pain, hypophosphatemia).

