#### 1.1.2 Secondary Objective:

- To evaluate the effects of BGJ398 on:
  - o mineral homeostasis
  - o quality of life
  - o muscle strength.
- To evaluate the effects of BGJ-398 on radiographic evidence of TIO.

**Table 1** summarizes the primary, secondary and exploratory objectives tagged with the associated endpoints and evaluation criteria:

	Objective	Endpoint Measures
Primary	Complete metabolic response	Normalization of blood phosphate and FGF23 off study drug
Secondary/Exploratory	Pharmacodynamics of mineral homeostasis response to BGJ398 in TIO	Changes in FGF23 (intact and C-terminal), Phosphorous, 1, 25 (OH) 2 vitamin D; TRP, TmP/GFR
	Effects on quality of life	Standardized measures of QoL
	Effects on muscle strength	Standardized muscle strength testing
	Effect on radiographic evidence of TIO	Changes in clinically-indicated FDG-PET/CT, octreotide SPECT/CT, or  Ga-DOTATATE PET/CT scan
	Assess safety/tolerability	Percentage of patients who incurred grade 3 or 4 adverse events (AEs) or serious adverse events (SAE) or AEs causing dose interruption/reduction

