### **3.7 SURGICAL GUIDELINES: NOT APPLICABLE**

### **3.8 RADIATION THERAPY GUIDELINES: NOT APPLICABLE**

### **3.9 COMPENSATION: NOT APPLICABLE**

### **3.10 CRITERIA FOR REMOVAL FROM PROTOCOL THERAPY AND OFF STUDY CRITERIA**

#### **3.10.1 Criteria for permanent removal from protocol therapy**

Subjects will be informed that they may choose to withdraw or the investigator may remove them from BGJ398 if it is in their best interest or if the subjects are unable to complete the required assessments and/or treatment. Voluntary withdrawal from the protocol is always an option for research participants.

The following conditions will require the permanent withdrawal of a subject from the BGJ398 therapy:

- Pregnancy
- Decline in calculated GFR to  $\leq 25$  mL/min/1.73 m^2 or decline in calculated GFR by 25 mL/min/1.73m^2 without clear etiology that persists on three monthly measurements (measured at the NIH or the subject's local laboratory).
- CTCAE  $\geq$  Grade 4 abnormalities in hepatic transaminases (ALT and AST)
- Treatment failure as defined by a blood phosphorus level below the lower limit of normal while taking the maximum tolerated dose of BGJ398 on two consecutive cycles.
- Investigator judgment based on subject's best medical interest

Subjects who require permanent discontinuation of BGJ398 therapy due to an adverse event will continue to be followed in the study until the toxicity has resolved or up to 30 days after study drug discontinuation. Pregnancies will be recorded from the time written informed consent is obtained until the subject is withdrawn from the study. Subjects who become pregnant during the study will be taken off BGJ398 and will be followed (with the subject's permission) until a pregnancy outcome is reached. The subjects will be referred to a physician outside of NIH for care. If the pregnancy results in anything other than a normal birth or elective abortion of a healthy fetus, it will be reported as an SAE. At the end of the pregnancy follow-up period, the subjects will be withdrawn from the trial.

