### **6.3.4 Duration of Response**

Duration of overall response: If complete metabolic response is achieved at the end of the 1 week end-of-study pharmacodynamic period (see section 3.4) following 24 weeks of BGJ398, the subjects will be followed for an additional 11 weeks ( $\pm$  2 weeks). If the subject has not had complete metabolic response at the end the 1 week end-of-study pharmacodynamic period or at any time during the follow-up, he/she will be offered the option of entering the extension phase or referred for alternative treatments.

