## 7 SAFETY REPORTING REQUIREMENTS/DATA AND SAFETY MONITORING

### 7.1 DEFINITIONS

#### Adverse Event

An adverse event is defined as any reaction, side effect, or untoward event that occurs during the course of the clinical trial associated with the use of a drug in humans, whether or not the event is considered related to the treatment or clinically significant. For this study, AEs will include events reported by the patient, as well as clinically significant abnormal findings on physical examination or laboratory evaluation. A new illness, symptom, sign or clinically significant laboratory abnormality or worsening of a pre-existing condition or abnormality is considered an AE. All AEs must be recorded on the AE case report form. All AEs, including clinically significant abnormal findings on laboratory evaluations, regardless of severity, will be followed until return to baseline or stabilization of event. Serious adverse events that occur more than 30 days after the last administration of investigational agent/intervention and have an attribution of at least possibly related to the agent/intervention should be recorded and reported as per sections 7.2, 7.4, 7.5.

An abnormal laboratory value will be considered an AE if the laboratory abnormality is characterized by any of the following:

- Results in discontinuation from the study
- Is associated with clinical signs or symptoms
- Requires treatment or any other therapeutic intervention
- Is associated with death or another serious adverse event, including hospitalization.
- Is judged by the Investigator to be of significant clinical impact
- If any abnormal laboratory result is considered clinically significant, the investigator will provide details about the action taken with respect to the test drug and about the patient's outcome.

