### 8.5 SAMPLE SIZE JUSTIFICATION

The sample size of 10 is based upon the highest enrollment that can be reasonably expected. Tumor-induced osteomalacia (TIO) is a very rare neoplastic syndrome; it is expected that only 10 patients will be found within the recruitment period and population that are eligible for enrollment.

The primary study endpoint is the complete metabolic response rate with its 95% confidence limit (95% CL). Patients withdrawing for any reason any time after receiving their first dose of study drug will remain in the ITT population and be counted as a treatment failure. Table 8.4 lists the resulting exact 95% CL for each of the possible response rates for sample sizes of 9 and 10. It is hypothesized that BGJ398 will be effective therapy in 40-60% of the subjects, based on the previous observation that 40-60% of TIO tumors harbor the fibronectin-fibroblast growth factor receptor-1 (FN1/FGFR1) fusion gene. A 60% complete response rate at N=10 would result in a lower 95% confidence bound of 26%. A lower 50% complete response rate at N=10 would still give a lower 95% confidence bound of 18.7% for the complete response rate. Finally, if the target population could not be reached with the final sample size being just 9 and with only 5 of 9 patients having a complete response (55.5%), the lower bound of the 95% CL for the complete response rate would be 21.1%. All three of these lower 95% CL boundaries of the complete response rates: 18.7, 21.1, and 26.2%, could justify BGJ398 therapy for patients with TIO depending on the risks relating to toxicity.

Table 8.4. Listing of the exact 95% confidence limits that would be obtained for each possible complete response rate with study's sample sizes of 9 and 10. The exact 95% confidence limits are based upon the binomial distribution.

Sample Size N=10		Sample size N=9	
Complete Response Rate (%)	Exact 95% CL* (%)	Complete Response Rate (%)	Exact 95% CL* (%)
0	(0.00, 30.8)	0.0	(0.00, 33.6)
10	(0.25, 44.5)	11.1	(0.28, 48.3)
20	(2.5, 55.6)	22.2	(2.8, 60.0)

Abbreviated Title: BGJ398 in TIO  
Version Date: 21MAY2019

30	(6.7, 65.3)	33.3	(7.5, 70.1)
40	(12.2, 73.8)	44.4	(13.7, 78.8)
50	(18.7, 81.3)	55.6	(21.1, 86.3)
60	(26.2, 87.8)	66.7	(29.9, 92.5)
70	(34.8, 93.3)	77.8	(40.0, 97.2)
80	(44.4, 97.5)	88.9	(51.8, 99.7)
90	(55.5, 99.8)	100.0	(66.4, 100.0)
100	(69.2, 100.0)		

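### Non-responders who complete 24 weeks and do not enter the extension leave about 1 week after the last dose with no later scheduled contact, while sustained responders are observed for about 12 weeks, so detection of new post-treatment adverse events depends on response

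*Combined protocol and SAP*

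**What the plan says.** **Follow-up of responders.** Section 3.1 says that "patients who appear to have had a complete metabolic response will be evaluated at the NIH every 4 weeks for 3 additional visits". Section 6.3.4 says that after a complete metabolic response at the end of the 1-week pharmacodynamic period "the subjects will be followed for an additional 11 weeks", with a tolerance of 2 weeks either way.

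**Exit of the others.** Non-responders whose phosphate normalized on drug are offered the extension (3.1.3), which has monthly calls and laboratory tests. Under section 3.1, patients who have not responded, have had significant side effects, or "do not want to continue in the extension phase, will be terminated from the study and referred for other treatment". No later visit or call is scheduled for them.

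**Adverse-event rules after the last dose.**
- Section 3.10.1: "Subjects who require permanent discontinuation of BGJ398 therapy due to an adverse event will continue to be followed" until the toxicity resolves or for up to 30 days. This covers only patients who stop because of an adverse event.
- Section 7.1 follows every existing adverse event to baseline or stabilization. "Serious adverse events that occur more than 30 days after the last administration" are to be recorded and reported if at least possibly related.
- Section 7.5.4 requires each serious adverse event to be reported within 24 hours of the investigator learning of it, whatever its cause.
- The definitions under section 6.3 start toxicity evaluability at first treatment and give no end.

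**Safety endpoint.** Table 1 in section 1.1.2 gives "Percentage of patients who incurred grade 3 or 4 adverse events (AEs) or serious adverse events (SAE"), or adverse events causing dose interruption or reduction. No time window is stated, and section 8 contains no safety analysis.

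**Text that points the other way.** The Précis describes 3 months of off-drug follow-up, section 6.3.3.3 determines best overall response at 9 months, and the schedule of events runs through V13 to V18. None of these is limited to responders.

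**The concern.** A crude percentage of patients with an event is interpretable only if patients are watched for a comparable, stated time. Here the time after the last dose is set by the efficacy outcome. If delayed events occur, they are more likely to be found in a responder than in a patient who left after a week, so the reported percentage partly reflects the response rate.

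Delayed ocular events show what could be lost. Apart from examinations done when clinically indicated, section 2.5 places the only off-drug eye examination at week 36, which a patient terminated at about week 25 does not reach. Section 11.1.2 notes that in earlier experience eye follow-up after end of study was inconsistent. With 10 patients, one undetected event changes the percentage by 10 points.

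**Working it through.** **1. The plan's own follow-up length.** Section 8.3 names a 12-week follow-up. From 6.3.4: 1 + 11 = 12 weeks (10 to 14 with the tolerance). From 3.1: 3 visits × 4 weeks = 12 weeks. 24 + 12 = week 36. The figure reproduces.

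**2. Time of exit for non-responders.** Section 3.4 specifies up to 7 draws, about daily, after the last dose. Sections 3.1.3 and 6.3.4 judge response at the end of that week. Exit is therefore at about day 7. Section 3.1 read alone would place it at the end of week 24, so about 1 week is the longer of the two readings.

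**3. Does another rule cover day 8 onward?** Section 3.10.1 does not apply, because these patients completed treatment. The stabilization rule in 7.1 covers events already present. The late-event rule in 7.1 and the reporting rule in 7.5.4 cover serious events that become known. None schedules a contact that would find a new event.

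**4. Size of the gap, using 30 days as the reference.** No general 30-day collection window is stated. It is inferred from the boundary in 7.1 and the period in 3.10.1.
- Off-drug days without scheduled contact: 30 − 7 = 23; 23/30 = 77%.
- Treatment plus 30 days: 24 × 7 + 30 = 198 days. Observed: 168 + 7 = 175; 175/198 = 88%. Missing: 23/198 = 12%.
- Against the full 36 weeks (252 days): 175/252 = 69% observed.

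Table 1 counts on-drug events as well, so the 12% describes the endpoint better than the 77%.

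**5. Upper bound on the imbalance.** Inputs are section 8.5: "The sample size of 10 is based upon the highest enrollment that can be reasonably expected", and "It is hypothesized that BGJ398 will be effective therapy in 40-60% of the subjects". Suppose all 10 patients complete treatment, no non-responder enters the extension, responders contribute 12 weeks and the rest 1 week.

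| Responders | Off-drug person-weeks | Share from responders |
|---|---|---|
| 4 | 4×12 + 6×1 = 54 | 48/54 = 89% |
| 5 | 5×12 + 5×1 = 65 | 60/65 = 92% |
| 6 | 6×12 + 4×1 = 76 | 72/76 = 95% |

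Extension entrants leave this table, so the true number affected is smaller and cannot be calculated from the documents.

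**6. Illustration, with assumed risks.** The documents give no rate of delayed events. Assume a constant hazard and a 12-week post-drug risk P; the risk over w weeks is 1 − (1 − P)^(w/12). The last column takes 5 of 10 responders and no extension entry: (5 × P + 5 × 1-week risk)/10.

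| Assumed 12-week risk | Over 1 week | Over 30 days (30/7 weeks) | Expected observed, all 10 |
|---|---|---|---|
| 10% | 0.9% | 3.7% | 5.4% |
| 20% | 1.8% | 7.7% | 10.9% |
| 30% | 2.9% | 12.0% | 16.5% |

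Under these assumptions the expected proportion with a post-drug event is a little over half of the assumed risk. This concerns the post-drug component alone.

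**The case against.** **Most adverse events arise on drug.** Every completer has the same 24-week treatment period, and dose interruption or reduction can occur only on drug. This stands, and it is why the gap is better put at 12% than at 77%.

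**Existing safeguards do much of the work.** Known events are followed to stabilization and serious events are reportable once learned of. This stands. The remaining gap is new events that nobody volunteers, mainly non-serious ones. A grade 3 event need not be serious, so Table 1 is still exposed.

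**Few patients may be affected.** Both earlier patients with this disease described in section 1.2 had their phosphate corrected on drug, which is the condition for the extension offer. Patients with persistently low phosphorus at their maximum tolerated dose meet the treatment-failure rule in 3.10.1, so some never complete 24 weeks. A reader might infer from the hypothesized 40-60% response rate that 4 to 6 of 10 patients fall in the gap. The documents do not support that, because extension uptake is not given.

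**No comparison is distorted.** The trial has one arm, and section 8.2 plans no sub-analyses. This stands.

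**The documents may intend 3 months for everyone.** The Précis, 6.3.3.3 and the schedule can be read that way. Section 3.1 is more specific, but the texts conflict. This objection turns part of the point into a need for reconciliation and does not remove it.

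**Conclusion.** The point holds in a limited form. For completers without a complete metabolic response who do not enter the extension, the plan schedules no detection of new adverse events after about day 7, against about week 12 for sustained responders. A responder who loses response may also leave or enter the extension earlier. The gap is about 23 of the first 30 post-dose days, or about 12% of treatment plus 30 days, for an unknown number of patients. The post-treatment part of the windowless Table 1 percentage therefore depends on response.

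Two stronger readings are not supported. A reader might infer that the plan already requires event collection to day 30 for everyone and then breaks its own rule; section 7.1 only implies a boundary for late serious events. A reader might also infer that the patients lost are those on the highest dose, since escalation follows unsuppressed FGF23. But escalation under 3.1.2 rests on on-drug FGF23 at weeks 6 and 14, previously treated patients start at their last dose, and complete response is judged off drug. A patient suppressed on the starting dose who relapses off drug is a non-responder who never escalated.

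This is a cheap improvement to safety ascertainment. It does not touch the primary analysis.

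**What to change.** 1. In section 3.1 and the off-study criteria, state one adverse-event collection window after the last dose for every treated patient who does not resume drug. Thirty days is a natural choice because it matches the boundary implied in 7.1 and the period used in 3.10.1. Schedule a telephone contact at its end, as the extension phase already does monthly. The wording should also cover patients who stop early for reasons other than an adverse event.
2. In section 8, define the Table 1 safety percentage on treatment plus that window. List later events in responders and extension-phase events separately. For patients who resume drug, close the window at resumption and state how many this applies to.
3. Reconcile the Précis, section 6.3.3.3 and the V13 to V18 columns of the schedule with the termination rule in 3.1, so that it is clear whose off-drug follow-up runs to week 36.

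If all 10 patients completed the common window, off-drug observation would be 10 × 30/7 = 43 person-weeks whatever the response rate. The cost is protocol wording and one call per non-extension patient. No dose, treatment or extension rule changes.
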